## Aim 1 Analyses.

### Plasma Nicotine

The main plasma nicotine outcome was the change in plasma nicotine concentration from before the 10-puff bout to after (i.e., nicotine boost) at the final clinical laboratory session (Fri, week 2; session 4, study day 12). Plasma nicotine boost was calculated for each participant by subtracting their pre-puff plasma nicotine concentration from their post-puff plasma nicotine concentration at each session. Mann-Whitney U tests compared the participant-level nicotine boost estimates across the IQOS-M and IQOS-T groups (Stata 17).

Exploratory analyses compared within-group differences in nicotine boost between sessions 3 (Mon, week 2; study day 8) and 4 (Fri, week 2; study day 12) using Wilcoxon Signed Rank tests. Differences in nicotine boost between OB menthol cigarettes (Fri, week 1; study day 5) and IQOS (Fri, week 2; study day 12) were assessed within each group using Wilcoxon Signed Rank tests. Pre- and post-puff plasma nicotine concentrations at each session were compared within-group using Wilcoxon Signed Rank tests to determine if pre- and post-puff plasma nicotine concentrations differed.

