#### Primary Study Endpoints:

*Aim 1:* For sub-hypothesis A, the outcome is the baseline-adjusted plasma nicotine concentration following a 10-puff directed bout with the participant's randomly assigned IQOS product on Friday of the intervention week. For sub-hypothesis B, the outcome is the average duration of the puffs taken during the 10-puff directed puffing bout with the participant's randomly assigned IQOS product on Friday of the intervention week. For sub-hypothesis C, the outcome will be the degree of cigarette craving suppression from before to after the directed puffing bout with the participant's randomly assigned IQOS product on Friday of the intervention week. Sub-hypothesis D will consider differences in IQOS' cross-price-elasticity obtained during the ETM performed on Friday of the intervention week between those with access to IQOS-M and IQOS-T and those with

access to IQOS-T only. Sub-hypothesis E will compare the baseline-adjusted plasma menthol-glucuronide following a 10-puff directed bout between IQOS-M and IQOS-T groups on Friday of the intervention week.

*Aim 2:* The primary EMA outcome (H2A) is the percentage reduction in average daily consumption of cigarettes (Tues-Thurs) from the baseline to the intervention week (e.g., 10 cigs/day in baseline week to 2 cigs/day in intervention week = 80% reduction). The outcome for H2B is the average daily number of IQOS HeatSticks used on Tues-Thurs of the intervention week. The outcome for H2C is the percentage of average daily consumption of tobacco products (cigarettes + IQOS) consumed during the intervention week (Tues-Thurs) that are IQOS HeatSticks.

- 2. Overview of Design. Once enrolled, eligible participants will complete a two-arm, parallel group, 14-day clinical lab study (Aim 1) of IQOS that includes naturalistic assessment (Aim 2; see Table 1). First, participants will complete a 7-day positive-control, own-brand (OB) menthol cigarette baseline. Then, for the second 7-day period, participants will be randomized (1:1 allocation; stratified by gender (Male vs Female) and race (African American/Black vs non-African American/Black) to receive either IQOS-M or IQOS-T and instructed to attempt to use their assigned product as a complete cigarette substitute. The baseline and intervention weeks will feature clinical lab sessions (Monday and Friday) and daily naturalistic use assessments.

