# 6. Study Procedures.

[figure not shown]
The study is divided into 3 phases: Screening/Enrollment, Baseline Week (use OB menthol cigarettes), and Intervention Week (use randomly-assigned) IQOS product. In the Screening/Enrollment phase, participants will complete the CSTP/BHRL registry to assess initial eligibility for this study and those deemed potentially eligible will be invited to an in-person screening session at the CSTP. At this session, informed consent will be obtained, eligibility confirmed, and baseline/demographic information collected. At the end of the in-person screening session, all eligible and consenting participants will be given an opportunity to take 4 test puffs of the IQOS product (flavor: Tobacco). During the baseline and intervention weeks, participants will complete clinical lab sessions (see "Aim 1" below) and naturalistic use assessments (see "Aim 2" below). Please note, at the start of each in-person activity, participants will answer 4 questions to screen for COVID-19 as with the CSTP's other ongoing projects (all answers must be "no" in order to continue). Randomization will occur at the beginning of the first clinical lab session (Monday, Baseline week) to allow for the proper ETM to be displayed during all subsequent sessions.

	Pre- screen	Screen	Mon	Tues -Thurs	Fri	Sat-Sun	Mon	Tues-Thurs	Fri	Sat-Sun
Week	NA	0	1	1	1	1	2	2	2	2
Phase	Screening/Enrollment Baseline Week (Own-Bra			nd Menthol Cigarettes)		Intervention week (IQOS-menthol or IQOS-tobacco)				
Main Activity	Online Survey	In-person screening + Test Puffs	Lab Visit 1 + Randomization	Natural Use (EMA)	Lab Visit 2	Natural Use (EMA)	Lab Visit 3 + IQOS Distribution	Natural Use (EMA)	Lab Visit 4	Natural Use (EMA)
Time	10 min	60 min	120 min	3 min/day	120 min	3 min/day	120 min	3 min/day	120 min	3 min/day
Relevant Measures	Baseline Demographics, Health, and Tobacco Use		Aim 1	Aim 2	Aim 1	Aim 2	Aim 1	Aim 2	Aim 1	Aim 2

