Aim 1: During the course of the clinical lab study set forth in Aim 1, participants will complete directed puffing bouts (10-puffs, 30 second interpuff interval) with either OB (baseline week) or their randomly-assigned IQOS product (intervention week). The interpuff interval is defined as the time between the start of 1 puff and the beginning of the next (Hiler et al., 2017). This procedure requires physiological monitoring of heart rate and blood pressure (sessions will be stopped if blood pressure ever exceeds 180/120) and venipuncture and/or catheter placement will be completed by [name], RN. One blood sample (7 mLs) will taken immediately before and immediately after a standard, controlled 10-puff directed puffing bout (total of 14 mL per session). A total of 56 mL of blood will be sampled for the entire study; this amount of blood sampling will occur at 4 sessions over a 12 day period and is less than a standard blood donation that is provided in a single sitting (473 mL). Outcome measures include changes in plasma nicotine and menthol concentration from pre- to post- puffing bout and subjective effects, including cigarette craving suppression as well as the direct effects of OB and IQOS. Following this procedure, participants will then complete an Experimental Tobacco Marketplace (ETM). In the ETM, participants will be asked to make purchasing decisions across an array of tobacco/nicotine products, including IQOS and OB, as their OB become increasingly expensive (prices will be presented in random order at each session [i.e., the order of pricetrials will be randomly determined for each session, but within a session each participant will face the same order of price-trials]). The minimum task time for the ETM will be set to 20 minutes (i.e., if a participant finishes all questions in the ETM before 20 minutes, they'll cannot progress to the next portion of the session until 20 minutes has elapsed). The primary outcome of interest is the cross-price elasticity of demand for IQOS as a function of OB price. Each session will begin by obtaining an exhaled Carbon Monoxide breath sample, as will be done in the in-person screening session, and asking participants whether they've abstained from using tobacco or nicotine products in the last 8 hours. Moreover, on the 2 Friday sessions, participants will complete a short "timeline follow back" assessment to report on their usage of cigarettes, IQOS, and other tobacco products during the preceding 3-days (Tues-Thurs). A timeline of session structure is provided below.

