
Though every effort will be made to have participants complete the study on the prescribed timeline (in-person screening, 2 baseline week visits [Mon, Fri], 2 intervention week visits [Mon, Fri]), we recognize that things outside the participant's or the researcher's control could impact completion of the study on this schedule. Thus, to handle the event in which a participant misses a session, we have devised the following plan. If an in-person screening session is missed, that session will be rescheduled at the participant's convenience. If the participant misses 1 of the baseline week visits, we will NOT reschedule the missed session – the single baseline visit that was completed will be used as the control comparison in statistical analyses. If both baseline visits are completed, the Friday results will be used as the control comparison. If a participant misses their Monday intervention week visit, we will reschedule for the next Monday on which the participant is available and commence the week as normal from that point. If a participant misses their Friday intervention week visit, we will reschedule for the next business day on which the participant is available. Friday intervention week sessions will not be rescheduled such that the "naturalistic" use period is any less than 3 full days (i.e., the rescheduled session will occur the following week).

Aim 2: In addition to the clinical lab sessions, participants will report usage of OB and their randomly assigned IQOS product daily by responding to ecological

momentary assessment (EMA) prompts (text or email) sent each morning of the 2-week study window. Surveys will be sent at 8 AM each day; if a participant has not responded by noon a reminder text/email will also be sent. Outcomes are primarily concerned with responses to EMA prompts on Tuesday, Wednesday, and Thursday of each week – but prompts will be sent daily to encourage habit formation and compliance. Participants will use their OB during the baseline week.

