### $log(Demand) = \beta_0 + \beta_1 log(OB Menthol Cigarette Price) + e,$

where  $\beta_0$  represented the cross-price intensity of demand,  $\beta_1$  represented the CPE of the fixedprice alternative as a function of OB menthol cigarette price (main outcome), and *e* was the error term. Mann-Whitney U tests compared the individual-level CPE estimates for IQOS across participants with access to both flavors of HeatSticks (IQOS-M group) to participants with access to only Regular/Tobacco HeatSticks (IQOS-T group) at the final clinical laboratory session (IQOS; Fri, week 2; session 4, study day 12). As an alternative strategy for calculating CPE estimates, demand for each fixed-price alternative was averaged within-group at each price trial in the ETM then a single regression for each group was fit to Equation 1. The resulting  $\beta_1$ coefficient estimates were compared across experimental groups using a linear combination of parameters approach.

To ensure data quality and that participants were responding to the price cues within the task, demand for OB menthol cigarettes in the ETM was modeled using an exponentiated demand equation (GraphPad Prism 9; Hursh & Silberberg, 2008),

$$Q = Q_0 + 10 * k (e^{(-\alpha(C * Q_0))}) - 1),$$

where *C* represented the cost of the OB menthol cigarettes, *Q* represented cigarette consumption at price *C*, *Q*0 represented OB menthol cigarette demand intensity (i.e., cigarette consumption at the lowest price trial), *k* represented the range of cigarette demand across price trials in log units, and  $\alpha$  was the free parameter that represented the rate of change in demand elasticity. *k* was set equal to 4.89 for all participants (Hursh & Roma, 2013; Hursh & Silberberg, 2008; Quisenberry, Koffarnus et al., 2016). Group-level averages for  $\alpha$  and R^2 were the outcomes of interest;  $\alpha$  was expressed in terms of log( $\alpha$ ) because  $\alpha$  values tend to be very small. OB menthol cigarette demand was also assessed for each participant using criteria (i.e., trend, bounce, reversal from zero) for identifying nonsystematic demand in purchase tasks (Stein, Koffarnus et al., 2015).

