# Aim 2 Analyses.

### Naturalistic Use

The main naturalistic use outcome was the percentage reduction in the mean number of cigarettes smoked per day from the baseline week (Tues-Thurs, week 1) to the intervention week (Tues-Thurs, week 2) based on responses to EMA prompts. The percentage reduction in mean number of cigarettes smoked per day was calculated for each individual as (Stone, DeAtley et al., 2022):

% reduction in cigarettes consumed per day =  $100 \times (\frac{Avg \# menthol \ cigarettes \ per \ day_{Week \ 1, \ Tues-Thurs} - Avg \# menthol \ cigarettes \ per \ day_{Week \ 2, \ Tues-Thurs})}{Avg \# menthol \ cigarettes \ per \ day_{Week \ 1, \ Tues-Thurs}})$ 

Percentage reductions in OB menthol cigarette consumption from the baseline week to the intervention week were compared across the IQOS-M and IQOS-T groups using Mann-Whitney U tests. As sensitivity analyses, statistical comparisons were repeated using responses to the three-day TLFBs conducted at sessions 2 (OB, Fri) and 4 (IQOS, Fri) and by imputing missing EMA values with multiple imputation by chained equations (i.e., predictive mean matching based on five nearest neighbors across 10 imputed datasets). Exploratory analyses compared mean daily use of IQOS HeatSticks (Tues-Thurs) during the intervention week across the IQOS-M and IQOS-T groups using Mann-Whitney U tests. Within-group differences in total tobacco consumption (i.e., sum of IQOS and OB consumption), OB cigarette consumption, and IQOS consumption during week 1 compared to week 2 were evaluated using Wilcoxon Signed Rank tests.

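### The primary between-arm tests ignore the gender and race strata, and the H1A nicotine test also leaves out the own-brand boost measured in week 1; the tests are valid but give up precision, chiefly for H1A

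*Combined protocol and SAP*

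**What the plan says.** Section 2 (Overview of Design) describes the allocation as "1:1 allocation; stratified by gender (Male vs Female) and race (African American/Black vs non-African American/Black". Section 1 names H1A, H1D and H2A as the primary outcomes. Their between-arm tests, in Section 9, are:

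- **H1A**, Plasma Nicotine: "Mann-Whitney U tests compared the participant-level nicotine boost estimates across the IQOS-M and IQOS-T groups (Stata 17".
- **H1D**, Experimental Tobacco Marketplace (ETM): "Mann-Whitney U tests compared the individual-level CPE estimates for IQOS across participants with access to both flavors of HeatSticks (IQOS-M group", set against the tobacco-only group.
- **H2A**, Naturalistic Use: percentage reductions in cigarettes "were compared across the IQOS-M and IQOS-T groups using Mann-Whitney U tests".

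No stratum or covariate term appears in these tests, in the group-level alternative for H1D, or in the sensitivity analyses for H2A.

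Nicotine boost is calculated at every session, so each participant has an own-brand value from week 1. The planned own-brand versus IQOS differences "were assessed within each group using Wilcoxon Signed Rank tests". Section 6 has a rule for a missed week-1 visit: "the single baseline visit that was completed will be used as the control comparison in statistical analyses". If both visits were attended, the Friday one is used.

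The Primary Study Endpoints text calls the H1A outcome baseline-adjusted. Sections 6 and 9 show that this means post-puff minus pre-puff within the same session. It is not an adjustment for week 1.

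**The concern.** If gender and race matter enough to stratify on, an analysis that ignores them leaves their variance in the error term. The test then tends to be conservative. A participant's boost from a standard ten-puff bout on their own cigarette may also predict their boost from the same bout on IQOS. Where it does, leaving it out of the between-arm comparison costs power and leaves chance imbalance uncorrected.

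The within-arm Wilcoxon tests have their own purpose: they address the part of H1A which says that both IQOS products deliver less nicotine than own brand. They say nothing about the difference between the flavours.

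H1A has the most at stake. Section 9 sizes the trial on plasma nicotine, and its assumed effect (d=0.76) is the smallest of the three (1.16 for ETM, 2.66 for cigarette reduction). H2A already uses its week-1 value through the percentage reduction.

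**Working it through.** **Inputs from the documents.** 25 per arm (Section 3); alpha 0.05, target power 0.80, and d of 0.76, 1.16 and 2.66 stated as lower bounds (Section 9).

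**Assumptions not in the documents.** Sidedness; the correlation r between own-brand and IQOS boost; the share R² of outcome variance explained by the strata; permuted blocks of four; a normal outcome; no missing data.

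**1. The plan's own figure.** Section 9 gives N=50 for power of at least 0.80 at d=0.76. Mann-Whitney power is taken as that of a t-test with the sample size multiplied by 3/π (normal outcome).

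- One-sided: N=48 is required, and power at 25 per arm is 0.827. The stated 50 is reproduced.
- Two-sided: N=60 is required, and power at 25 per arm is 0.729. The stated 50 is not reproduced.

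**2. What the covariate is worth on variance alone.** Adjustment multiplies the residual variance by 1 − r², so 25 per arm behaves like 25/(1 − r²) per arm unadjusted:

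- r=0.3: 25/0.91 = 27.5
- r=0.5: 25/0.75 = 33.3
- r=0.7: 25/0.51 = 49.0

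**3. Power for H1A by simulation.** Settings: d=0.76, two-sided 5%, 4,000 trials per cell, Monte Carlo standard error about sqrt(0.72×0.28/4000) = 0.007. The adjusted test is a regression of outcome ranks on arm, rank of own-brand boost, gender and race.

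| r | Mann-Whitney, R²=0 | Adjusted, R²=0 | Mann-Whitney, R²=0.10 | Adjusted, R²=0.10 |
|---|---|---|---|---|
| 0 | 0.72 | 0.72 | 0.74 | 0.76 |
| 0.3 | 0.71 | 0.75 | 0.73 | 0.80 |
| 0.5 | 0.73 | 0.82 | 0.73 | 0.87 |
| 0.7 | 0.71 | 0.93 | 0.73 | 0.96 |

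One-sided at R²=0, Mann-Whitney power is about 0.82, against about 0.82, 0.84, 0.90 and 0.97 for the adjusted test at the same four values of r.

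With the strata alone and no own-brand term, calculated two-sided power is 0.728, 0.750 and 0.772 at R² of 0, 0.05 and 0.10. The own-brand boost carries most of the possible gain.

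**4. Size under the null** (r=0.5, two-sided 5%). Mann-Whitney rejected in 4.4%, 4.1%, 3.5% and 3.2% of trials at R² of 0, 0.05, 0.10 and 0.20. With perfect balance within strata the formula is 2·P(Z > 1.96/sqrt(1 − R²)), which gives 3.9% at R²=0.10 and 2.8% at R²=0.20. The adjusted test rejected in 4.6%, 5.0%, 4.9% and 5.5%. So the planned test is valid and becomes conservative as the strata matter more.

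**5. Chance imbalance, as an illustration.** The between-arm difference in mean own-brand boost has standard error sqrt(2/25) = 0.283 SD. At r=0.5, an imbalance of one standard error moves the unadjusted difference by 0.5 × 0.283 = 0.141 SD, and 0.141/0.76 = 19% of the planned effect. This is the same precision loss seen another way, not an added harm.

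**6. H1D and H2A.** Two-sided Mann-Whitney power is about 0.975 at d=1.16 and above 0.999 at d=2.66. At R²=0.10, adding the strata raises the H1D figure to 0.985, a gain of one point. H2A has nothing left to gain.

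**The case against.** The strongest case against is that this is a preference about efficiency. An unadjusted rank test is valid in a small randomised laboratory study, and two of the three primary outcomes gain almost nothing.

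For H1A the gain depends on a correlation that the documents do not give, between two different products. At r=0.3 it is only a few points. In a run where arms were not balanced within strata, power was 0.73 unadjusted against 0.72 adjusted at r=0.2, and 0.72 against 0.73 at r=0.3. H1A is also worded directionally, and a one-sided Mann-Whitney test already meets the 0.80 target.

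Adjustment can also cost power if covariates are missing. With 10% of own-brand boosts missing and those participants dropped, power was 0.68 adjusted against 0.72 unadjusted at r=0.3, and 0.77 against 0.72 at r=0.5. Finally, Section 9 is written in the past tense, so the analysis may be done.

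Most of this stands as a limit on the size of the point. The gain is uncertain and may be small. It does not remove the point: the strata and the own-brand values are already in hand, and with the stratified allocation there is no material loss at r=0. The Section 6 rule for a missed visit limits missingness, but a participant with no usable own-brand pair still needs a rule. The past tense affects which analysis can be primary, not whether the adjusted one is worth reporting.

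A further objection is that the covariate is measured after randomisation: "Randomization will occur at the beginning of the first clinical lab session (Monday, Baseline week) to allow for the proper ETM to be displayed". Both arms nevertheless smoke their own brand throughout week 1, and IQOS is handed out only at the end of the Monday visit in week 2. The session-1 bout also comes before the first arm-specific ETM: "Following this procedure, participants will then complete an Experimental Tobacco Marketplace (ETM".

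**Conclusion.** The concern holds. The three primary tests ignore the randomisation strata, and the H1A test also leaves out the week-1 own-brand boost. No test is invalid and no hypothesis goes untested.

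For H1A, two-sided at d=0.76, the cost runs from nothing (r=0, strata unrelated to outcome) through about 10 points of power at r=0.5 to about 20 at r=0.7. If the test is one-sided, the planned power already exceeds 0.80 and the gain at r=0.5 is about 8 points. For H1D and H2A the cost in power is negligible, and the case there is consistency with the randomisation.

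The figures rest on assumed values of r, R², block size, normality and complete data. The change is worth making because it uses data and strata the trial already has.

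**What to change.** - **H1A.** Make the primary test a rank-based ANCOVA: regress the rank of session-4 boost on arm, rank of own-brand boost, gender and race. Use session-2 own-brand boost, or the single completed week-1 visit under the Section 6 rule. Add a rule, blind to arm, for anyone with no usable own-brand pair, such as the mean covariate rank pooled over both arms, so that nobody drops out of the test.
- **Timing.** State that session 2 follows randomisation but uses the same own-brand product in both arms. As a check, repeat the analysis with session-1 boost.
- **H1D and H2A.** Add gender and race, by the same rank regression without a week-1 covariate or by a stratified rank test (van Elteren). Do not adjust H1D for week-1 ETM results, because that menu already differs by arm.
- **Sensitivity.** Keep the plain Mann-Whitney tests, and state whether tests are one- or two-sided.
- **If outcomes have already been analysed.** Leave the planned tests as primary and report the adjusted analysis as a labelled supplement.

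The cost is SAP wording and a few lines of code, or one supplementary analysis. No new data are needed.

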#### Puff Topography

The main puff topography outcome was the average puff duration during the 10-puff directed use bout at the final clinical laboratory session (Fri, week 2; session 4, study day 12). Mann-Whitney U tests compared the mean puff duration during the 10-puff directed use bout across the IQOS-M and IQOS-T groups (Stata 17).

To assess whether puff topography patterns changed during the 5-day naturalistic exposure to IQOS, topography outcomes at session 3 (Mon, week 2; study day 8) and session 4 (Fri, week 2; study day 12) were compared within-group using Wilcoxon Signed Rank tests. Difference in topography outcomes between OB menthol cigarettes (Fri, week 1; study day 5) and IQOS (Fri, week 2; study day 12) were assessed within-group using Wilcoxon Signed Rank tests.

